- e. By bed time
- f. By the next morning
- g. Before the next scheduled dialysis session
- h. Did not recover before the next scheduled dialysis session
- i. Patient unable or declined to answer

Furthermore, the Chairside system will require completion of this question once a week before the staff member begins the dialysis session. The patient care technicians and nurses will be trained prior to study start to record these data.

Responses to this variable will also be used as a secondary outcome for patient symptoms, alone and in combination with the patient symptom burden measure described above. This question will be asked once per week of every patient in the study.

Quality of life. Quality of life is a patient-reported outcomes, which is “any report of the status of a patient's health condition that comes directly from the patient, without interpretation of the patient's response by a clinician or anyone else.”¹²⁷ PRO instruments can be interviewer-administered, self-administered, computer-administered or interactively administered.¹²⁷ We will use the 36-item Kidney Disease Quality of Life (KDQOL™-36 Version 1),^{128, 129} which has good internal consistency based on alpha scores.¹²⁹ This instrument is required annually for US hemodialysis patients.¹³⁰ The quality of life survey, the Kidney Disease Quality of Life (KDQOL™-36 Version 1), is intended to be completed on at least an annual basis. KDQOL results will be provided twice for each patient from surveys available as follows: 1) The latest survey within 12 months prior to the start of the study intervention and 2) the earliest survey within 12 months after the start of the intervention. As is current procedure at FMCNA, the measure of quality of life is based on a self-administered survey by providing a paper copy to the patient to complete during treatment or at home. If a patient needs assistance, the Social Worker will assist patients during treatment or via phone in completion of the survey as needed or desired.

Hospitalization. These data will be gathered from FMCNA records for all patients. Hospitalizations within the study period will be calculated. Secondary analyses of this outcome will assess hospitalizations by cause using hospital discharge diagnosis (e.g., fluid-related or cardiovascular causes, COVID-19), number of hospitalizations per patient, and length of hospitalization.

Mortality. These data will be gathered from FMCNA patient records.

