3.2.3 Behavioral Outcomes (Behavior Change Measures)

Patient session instability prevention behavior. Once per week, the patient care technician or nurse will also record data regarding patient participation in their fluid removal goals for a specific session. The question, which has already been incorporated into FMCNA's Chairside documentation system for study purposes, is as follows:

“Did the patient make a request today regarding their fluid removal goal?

- No
- Yes, requested more than the recommended fluid removal goal
- Yes, requested less than the recommended fluid removal goal”

Using these data, we will create a patient-level measure of instability prevention behavior that sums the number of requests regarding fluid removal made by each patient, along with weighting based on the appropriateness of the request. Appropriateness of the patient request will be determined based on the “direction of patient request” combined with assessment of clinical factors.

Fluid practice patterns measure. We will create a patient-level measure of fluid management practice patterns that combines the frequency of the following behaviors: (1) Number of times a patient's post-dialysis target weight was changed, (2) patient average treatment time delivered, (3) patient average session ultrafiltration rate, (4) number of changes in number and categories of BP medications patient is taking, (5) use of cool dialysate (based on average dialysate temperature for the session), and (6) whether the patient switched to home dialysis (peritoneal dialysis or home hemodialysis, using treatment modality change) during study period. These are practices that could change as a result of the interventions that may explain intervention effects in the primary and secondary outcomes.

3.2.4 Importance of secondary outcomes, and their role in the analysis and interpretation of study results

We will analyze the impact of the interventions on each of the secondary outcomes; thus, the effectiveness of the interventions will be assessed in relation to both the primary and the secondary outcomes. The study has the following patient-centered secondary outcomes:

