One wrinkle in the analysis of factorial designs is that interaction effects must be assumed to be null in order to test the main effects, but interaction effects are often of interest and are generally tested. Much has been written about this issue in the statistical literature; in practice, main effects are presented in the absence of a (statistically or clinically) significant interaction. When a statistically and clinically significant interaction is present, then the effect of each intervention is presented in the presence and absence of the other. Note that no other design can even test the presence of an interaction, so the simplicity gained by other analyses is at the cost of ignoring the possibility of interaction.

After the 12-week baseline period we plan to track outcomes for 36 weeks (24-week intervention period and 12-week post-intervention period). The parallel design with a 24-week intervention period, in assessing a post-intervention follow-up period, will generate valuable information related to the extent to which the intervention can sustain effects beyond an intensive implementation period. This meets the need for longer-term effectiveness studies of patient safety checklists.¹⁴⁷ This will also help clinics to understand an optimal schedule for intervention implementation.

III. Trial phase

The study is designed to be a cluster-randomized, pragmatic comparative effectiveness trial. As such, the trial will take place as part of routine HD care, with low-intensity patient follow-up and use of outcome data already gathered routinely by facilities.¹¹⁸ As such, this trial leverages unobtrusive existing electronic health record data to collect data regarding outcomes with the addition of two new data collection items to be collected through the electronic health record.¹⁴⁸

IV. Multi-center trial

The study will take place in 20 outpatient hemodialysis facilities operated by FMCNA. FMCNA has provided one site Principal Investigator for the complete study, since all sites are part of the same organization. All data from each of these facilities will be provided by FMCNA through its central corporate data warehouse, which aggregates data across FMCNA's digital documentation system. FMCNA will submit an IRB Authorization Agreement to cede IRB review and oversight to the University of Michigan.

V. Study Arms

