5.4 TREATMENT ASSIGNMENT PROCEDURES

5.4.1 Randomization Procedures

The 20 hemodialysis facilities will be randomized to the four intervention combinations of the 2x2 factorial design, assigning 5 facilities to each of the 4 combinations (both provider education and patient activation using peer mentoring; provider education alone; patient activation alone; and neither intervention). Facilities will be stratified by geographic region and socio-economic status to ensure treatment balance on those factors.

With regard to peer mentoring only, we will randomly select patients who are not vulnerable and have not opted out of the study in succession, until approximately 30 English-speaking patients in a facility accept peer mentoring. Patient randomization will be stratified by treatment shift. Every time a patient declines to participate, we will choose another patient randomly until the enrollment target is reached. Patients entering a facility randomized to the patient activation intervention during weeks 1-18 of the 24-week intervention period will be added to the list of patients eligible for peer mentoring from which patients are randomly selected for peer mentoring. We anticipate that 15-20% of patients in the study facilities will be replaced by new patients during the 11-month study period due to mortality, change in ESRD treatment modality (e.g., a kidney transplant), or changing facilities.

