A final type of attrition may be the possibility of missing data due to patients not completing the self-reported quality of life (KDQOL) survey or the patient symptom question regarding recovery time. For example, some participants may refuse to answer certain questions or may miss follow-up surveys. Where possible, we will note reasons for missing data by triangulating data sources to determine whether a patient has moved to another facility, or in accordance with two of our outcomes, been hospitalized or die. Although every effort will be made to collect these data, some missing surveys are still likely, particularly among those in ill health. We do not expect missing surveys to be associated with study arm, but missingness itself can be analyzed for treatment differences as a tertiary outcome measure. The sample in each cross-section will include living patients only, so death will not be a problem as it would be in a longitudinal QOL study. We believe that this approach, along with our conservative assumptions regarding sessions needed as described previously, will largely prevent missing data for our primary outcome, as well as two secondary ones. Death will be tracked as an outcome, although the trial is not powered to assess this as a primary outcome. Data on subjects who leave the study site, will be used until their time of departure from the study. In other words, we will not track data for patients after they transfer to a non-study facility.

We will compare the characteristics of those with missing data to those without missing data, to test whether characteristics are similar between the groups. In addition to complete case analyses, we will use state-of-the-art statistical methods such as likelihood approaches and multiple imputation to deal with missing data.¹⁶⁰ These sensitivity analyses will assess the robustness of the results to missing data.

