For the above analyses, the variables of primary interest are the main effects of the interventions. *Session-level* covariate adjustment will include: (1) weekday of session, (2) dialysis session shift, (3) average session blood flow rate; (4) average session dialysate flow rate, and (5) dialysate composition (sodium, potassium, magnesium). *Patient-level* covariate adjustment will comprise: (1) patient demographics (age, race, ethnicity, sex, employment, literacy, education level, language spoken); (2) time since first dialysis; (3) cause of ESRD, (4) treatment history; (5) total transplants; (6) vascular access type; (7) patient laboratory data (serum phosphorous, dialysis adequacy, anemia management (hemoglobin), iron indices (serum ferritin, serum iron), mineral metabolism indices (calcium, phosphate, PTH)); (8) comorbidity index; (9) individual comorbidities and comorbidities in combination, including COVID-19; (10) patient's heart rate variability (based on variability in heart rate (HR) during dialysis session (difference between the highest and lowest heart rates, standard deviation of the heart rate measures, the square root of the mean squared differences of successive heart rate measures); (11) patient medications (prescriptions medications administered outside of center or in-center (including ESA prescription, iron, antibiotics and vitamin D analog), and non-in-center prescriptions). Patient data will be censored while they are at COVID-19 isolation facilities. Regression diagnostics will be used to assess model fit. Checks for functional form of continuous adjustment covariates will be carried out and any transformations will be implemented prior to adding the intervention variables to the model.

Three secondary analyses are planned for this Aim. The first will test the treatment effects in a similar model but adding adjustment for any covariates found to be unbalanced between treatment groups in preliminary analyses. This has the ability to further adjust for important confounders of treatment effects, but because it will use data-driven covariate decisions that are subject to analysis bias, it will be interpreted with caution. The next secondary analysis will test the interaction between the two interventions to detect a possible synergistic or antagonistic

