Aim 2. Test and compare the effects of the two HD facility-level interventions on secondary patient-centered clinical outcomes, including: patient symptoms, fluid adherence, dialysis adherence, quality of life, hospitalizations and mortality over the same timeframe.

Aim 2 incorporates six outcome measures: (1) patient symptoms (including a patient burden measure, dialysis recovery time, and proportion of sessions with each symptom), (2), fluid adherence (inter-dialytic weight gain), (3) dialysis adherence, (4) quality of life, (5) hospitalization (all-cause and by specific cause), and (6) mortality (all-cause and by specific cause), with will be analyzed at the individual level and summarized at the facility level. Each

will use a model format appropriate to the outcome type, but will otherwise follow the model strategy, including the secondary analyses, described for Aim 2 above. This includes censoring of patient data while they are at another facility. The fluid adherence (Interdialytic weight gain), symptom and quality of life analyses, based on continuous outcome measures, will be carried out using mixed models (the MIXED procedure of SAS). Note that the quality of life analyses will be based on data from two time points, one before intervention and one during intervention, rather than session-specific data as analyzed for the other outcomes. Analyses of missed or shortened HD sessions will employ logistic regression for longitudinal data, as in Aim 2. Analyses of hospitalization and mortality will use logistic regression for individual level data. As part of these models, we will test IDH-related variables (e.g., recent IDH, frequency of IDH in the past month) as potential predictors. In each case, the appropriate regression diagnostics will be used to assess model fit.

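### Deaths and hospital admissions fall under a censoring rule suited to session-level outcomes, follow-up of them stops at transfer, and the planned logistic regression has no way to handle either

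*Combined protocol and SAP*

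**What the plan says.** All references are to the combined protocol and SAP.

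- **Section 11.4, Aim 1.** The censoring rule for the session-based primary outcome is narrow: "Patient data will be censored while they are at COVID-19 isolation facilities".
- **Section 11.4, Aim 2.** Six outcomes are listed, among them hospitalization and mortality, all cause and by cause. They are to follow the model strategy set out earlier, and the text adds: "This includes censoring of patient data while they are at another facility". No outcome is exempted. Hospitalization and mortality are then assigned to individual-level logistic regression. The near-identical Aim 2 text in Section 11.2 does not contain the censoring sentence.
- **Section 5.4.3** (the first rule is repeated under missing data in Section 11.4). "Data on subjects who leave the study site, will be used until their time of departure from the study". Section 5.4.3 restates this as "we will not track data for patients after they transfer to a non-study facility".
- **Section 3.2.2.** For hospitalization: "These data will be gathered from FMCNA records for all patients". COVID-19 is one of the causes named for the by-cause analysis. For mortality the text names the operator's patient records as the source and says nothing about coverage.
- **Section 3.2.3.** A switch to home dialysis is one component of the fluid practice patterns measure. Of these components the plan says: "These are practices that could change as a result of the interventions that may explain intervention effects in the primary and secondary outcomes".
- **Section 5.4.1.** Replacement of 15-20% of patients over 11 months is expected "due to mortality, change in ESRD treatment modality (e.g., a kidney transplant), or changing facilities".
- **Section 11.4, closing text for Aims 1 and 2.** The primary tests are intent-to-treat.

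**The concern.** Suspending data while a patient dialyzes elsewhere makes sense for IDH, weight gain, adherence, in-session symptoms and recovery time, because no study-clinic session takes place. Death and admission do not depend on a study-clinic session. Under the Aim 2 sentence, a patient sent to an isolation unit who is admitted or dies there has that event censored, although COVID-19 admission is a cause the plan intends to analyse.

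Stopping at transfer is a second loss. Changing clinic happens after randomization and may be related to health or to care received. Section 5.4.4 continues outcome collection for patients who stop the patient activation intervention, but Section 5.4.3 does not follow those who change clinic.

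The third problem is the model. A logistic regression on whether a patient died or was admitted has no place for partial follow-up, and the plan states no rule for leavers. The analyst must code them as no event or drop them. The working shows that the two choices bias the arm comparison in opposite directions when leaving differs by arm.

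Finally, the plan does not say whether follow-up for death and hospitalization ends when a patient switches to home dialysis. Section 3.2.3 treats that switch as something the interventions could change. If follow-up does end there, the loss could differ by arm.

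At stake are two secondary outcomes. Mortality is also one of the two outcomes Section 11.3 expects to report to the DSMB.

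**Working it through.** **The plan's own figures.** The plan states no power or expected event count for death or hospitalization, so there is no figure to reproduce. Table 5 concerns the primary outcome and is not affected.

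**Inputs from the documents.** 1,200 patients (Section 11.2); 36 weeks after baseline (Section 4.1); annual mortality 17.5% (Section 2.1.3), with 15-20% in Section 9.3; two hospitalizations per patient-year (Section 9.3).

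**Input not in the documents.** The proportion *L* who would leave alive within 36 weeks. The 15-20% turnover in Section 5.4.1 cannot supply it, because it includes deaths. Mortality alone over 48 weeks is 1 − 0.825^(48/52) = 16.3% (13.9% to 18.6% at 15% to 20% a year), which takes up most or all of that range. I therefore assume *L* = 2%, 5%, 10% and 15%.

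**Full follow-up.**
- Death hazard: −ln(0.825) = 0.192 per year; T = 36/52 = 0.692 years.
- Risk of death: 1 − exp(−0.192 × 0.692) = 12.47%, or about 150 deaths in 1,200 (128 to 172 at 15% to 20% a year).
- Any admission: 1 − exp(−2 × 0.692) = 75.0%. Total admissions: 1,200 × 2 × 36/52 = 1,662, ignoring deaths.

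**Follow-up stopped at departure.** With constant hazards, h_leave = −ln(1 − *L*)/T, and the observed risk is h_event/(h_event + h_leave) × [1 − exp(−(h_event + h_leave) × T)]. For *L* = 5%, h_leave = 0.0741 and the observed risk of death is (0.1924/0.2665) × 0.1685 = 12.16%. Missed deaths are 1,200 × (0.1247 − 0.1216) ≈ 3.7.

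| Leave alive (assumed) | Deaths missed | Share of deaths | Observed any-admission risk (full: 75.0%) |
|---|---|---|---|
| 2% | 1.5 | 1.0% | 74.4% |
| 5% | 3.7 | 2.5% | 73.5% |
| 10% | 7.4 | 5.0% | 72.0% |
| 15% | 11.3 | 7.5% | 70.4% |

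**Leaving that differs by arm, no true effect on death, leavers coded as no event.** Observed risks are 12.16% at 5% leaving, 11.85% at 10% and 11.53% at 15%.
- 5% v 10%: odds ratio (0.1185/0.8815)/(0.1216/0.8784) = 0.97.
- 5% v 15%: odds ratio 0.94.

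The arm that loses more patients looks better.

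**The same case, leavers dropped.** The share observed to leave first is h_leave/(h_event + h_leave) times the same bracket: 4.68% at 5% and 9.37% at 10%. Risk among those kept is 0.1216/(1 − 0.0468) = 12.76% and 0.1185/(1 − 0.0937) = 13.07%. The odds ratio is (0.1307/0.8693)/(0.1276/0.8724) = 1.03, so the arm that loses more patients now looks worse. The direction of the bias depends on a choice the plan does not make.

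**The case against.** - **The Aim 2 sentence may be shorthand** for the COVID-19 isolation rule in Aim 1. Section 2.3.1 explains absences from the home facility with dialysis adherence as its example, which is a session-level use. This reading is possible, but it does not remove the conflict: the sentence still covers hospitalization and mortality, and isolation stays are when COVID-19 admissions would be expected.
- **This is a disclosed pragmatic choice.** Section 7.3 says there is no special follow-up, patients are still analysed by assigned arm, and Sections 5.4.3 and 11.4 promise comparison of patients with and without missing data plus likelihood and multiple-imputation sensitivity analyses. That is partial mitigation. The main model for these two outcomes remains undefined for a leaver.
- **Data access may be limited.** A reader might infer from the data arriving "through its central corporate data warehouse" that nothing stands in the way of following transfers. That sentence in Section 4.1 concerns the 20 study facilities. Extraction runs between the start and stop dates of a study order (Section 7.2), and the data use agreement is an attachment not available here. This objection stands, so continued extraction needs confirmation.
- **Home dialysis.** A reader might infer that patients who switch to home dialysis are lost because the intervention worked. No section ends their follow-up. Section 5.4.1 is a forecast of turnover, not a data rule, and modality change is itself among the data supplied (Section 4.1). The plan is silent, and the silence is the gap.
- **Coverage and coding.** A reader might also infer that mortality is promised for all patients, or that leavers will count as alive. The coverage wording is written for hospitalization only, and no section says how leavers are coded.

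**Conclusion.** The point holds as an inconsistency and an analysis gap in two secondary outcomes. As written, the plan censors deaths and admissions during time at another facility and stops follow-up at departure. This contradicts the stated coverage of hospitalization, sits poorly with intent-to-treat, and feeds a model that cannot use censored follow-up.

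The likely size is modest. If 2% to 10% leave alive, about 1.5 to 7 of roughly 150 deaths (1% to 5%) are missed, and a 5% v 10% difference in leaving moves a null mortality odds ratio to about 0.97 or 1.03, depending on how leavers are handled. These figures rest on an assumed leaving rate and on leavers having the same risk as those who stay. They would be larger if leavers differ in risk or if leaving differs more by arm; the documents show neither. The primary outcome, its power and its alpha are untouched, and the plan itself says the trial is not powered for death. The change is worth making because it is cheap and removes a real contradiction.

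**What to change.** 1. **Section 11.4, Aim 2.** Limit the censoring for time at another facility to session-level outcomes: IDH, weight gain, dialysis adherence, in-session symptoms and recovery time. State that deaths and hospitalizations found in the operator's records during such stays are counted. Align the parallel text in Section 11.2.
2. **Section 5.4.3 and the missing-data text in Section 11.4.** Continue extracting death and hospitalization to the end of the facility's follow-up for patients who have not opted out and who transfer or change modality within the operator, subject to IRB and data-use-agreement confirmation. Say explicitly what happens after a switch to home dialysis.
3. **Model.** Some patients will still leave the operator. Replace the logistic regression with a time-to-event model for death and a rate model for hospitalization, both using time at risk and accounting for facility clustering.
4. **Reporting.** Tabulate departures by reason and arm.

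The cost is SAP wording, a later stop date for two data elements in an existing extract, and the approvals. Patients who leave the operator altogether are still lost from their departure onward.
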